# 16.2.2.4 Correlate baseline RPPM values with presence of atypia at month 12 and month 24:

We will combine data set of metformin and no-metformin groups (N = 88) and use the breasts as the sampling units in this analysis. The possible dependency in observations between the left and right breasts for each woman will be adjusted using the GEE approach.

The baseline RPPM value of each protein will be correlated with Masood cytology score at month 12 using a simple linear regression method. In a multivariate analysis, Masood score at month 12 will be regressed on the baseline RPPM value of each protein, group indicator, age, race, prior excisional biopsy, and baseline Masood scores. Similar analysis will be conducted using the change rate of Masood score between baseline and month 12 in place of Masood score at month 12.

The baseline RPPM value of each protein will be correlated with presence and absence of atypia at month 12. A total of 50 proteins will be tested, so that the significance of each protein will be adjusted for multiple testing by controlling the family-wise error rate (FWER) using the permutation method. We expect that about 60% of the women will have persistent atypia at 12 months. The 50 proteins were selected from a previous study so that they are expected to have reasonable effect sizes. Assuming that each woman contributes samples from only one breast and the proteins have correlation coefficient of 0.1, the multiple testing procedure controlling the FWER at 10% level by two-sided tests will have about 90% probability to detect 15 or more proteins if 25 of the 50 proteins have an effect size of 0.8 times SD [Jung and Young, 2011]. Since about 75% of women are expected to contribute samples from both breasts to the study, the real power for this analysis will be higher.

In a multivariate analysis, presence of atypia at month 12 will be regressed on the baseline RPPM value of each protein, group indicator, age, race, prior excisional biopsy, and baseline Masood scores.

A similar analysis will be conducted to correlate baseline RPPM value of each protein with Masood score and presence/absence of atypia at month 24.

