#### 1.3.7 Summary of Feasibility Data and Significance

Ultimately, the most effective way to reduce breast cancer mortality is to prevent breast cancer. Here we aim to conduct prevention trials using biomarker-guided efficacy evaluation with an agent that targets signaling pathway that is known to be activated in ER-breast cancer. Metformin is a well-tolerated, inexpensive, oral hypoglycemic agent and prescribed to over 120 million Type II diabetic patients worldwide, and is safe in pregnancy. While metformin is undergoing pilot clinical testing in women with breast cancer, metformin's mechanism of action is poorly understood. It is known that metformin targets Akt/mTor, AMPK, and promotes a secondary reduction in mitochondrial complex 1 and insulin signaling. However, there is also evidence that metformin may also target NF $\kappa$ B and IL6. Given the potential complexity of metformin, we need to be able to precisely track signaling pathways targeted by metformin prevention.

We have developed the scientific framework, biomarkers, and strategies to test the ability of targeted agents to eliminate cytologic atypia in high-risk women. Using our combined proteomic/tracking tools we can directly test in an individual woman 1) for activated signaling pathways, 2) whether the prevention agent eliminates cytologic atypia, and 3) if not, we can then identify additional signaling pathways that can be targeted. The ability to test whether a prevention drug is working in an individual woman allows us to rapidly deliver targeted prevention tailored to an individual woman.

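### The family-wise-controlled test of 50 proteins pools breasts with and without atypia at entry, so it cannot separate markers of persistence from markers of entry atypia

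*Combined protocol and SAP*

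**What the plan says.** Section 16.2.2.4 pools both arms (N = 88) and will "use the breasts as the sampling units in this analysis", with GEE for the two breasts of one woman. For the binary outcome it says: "The baseline RPPM value of each protein will be correlated with presence and absence of atypia at month 12". The multiplicity rule follows directly: "A total of 50 proteins will be tested", with significance adjusted by "controlling the family-wise error rate (FWER) using the permutation method". The power text then says: "We expect that about 60% of the women will have persistent atypia at 12 months", and, assuming one breast per woman and 25 of 50 proteins with an effect of 0.8 SD, "the multiple testing procedure controlling the FWER at 10% level by two-sided tests will have about 90% probability to detect 15 or more proteins". It adds that power will exceed this because about 75% of women give both breasts.

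A separate paragraph plans an adjusted model: "In a multivariate analysis, presence of atypia at month 12 will be regressed on the baseline RPPM value of each protein", together with arm, age, race, prior excisional biopsy and baseline Masood scores. No multiplicity control is stated there.

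Other sections determine which breasts are in the data:
- Section 3.3.1: the qualifying sample may come from one or both breasts.
- Schema footnote 2: the breasts aspirated before randomization are the ones aspirated at follow-up.
- Section 16.2.1.1: the number of breasts with atypia at baseline is a covariate, so it varies.
- Section 1.3.2: the two breasts of one woman agreed poorly in the group's previous study.

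**The concern.** At the level of the woman, presence of atypia at month 12 and persistence are the same thing, because every woman enters with atypia. At the level of the breast they differ. A breast that was clear at entry and is clear at month 12 counts as absence, although it had nothing to lose. Month-12 status across all breasts therefore partly encodes entry status. A protein that differs between atypical and clear breasts at baseline becomes associated with the outcome even if it says nothing about whether atypia resolves.

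The use of the protein list is at stake. Section 1.3.7 describes testing whether the agent eliminates atypia and says that "if not, we can then identify additional signaling pathways that can be targeted". A list containing markers of entry atypia would be a poor guide to that. The one analysis that removes the problem, the model with baseline Masood score, is not the one given family-wise protection.

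**Working it through.** **1. The plan's own power.** Inputs from 16.2.2.4: 88 women, one breast each, 60% with atypia, effect 0.8 SD, 50 proteins, family-wise level 10% two-sided, correlation 0.1.
- Non-centrality: 0.8 × √(88 × 0.6 × 0.4) = 3.68.
- Simulated max-T cutoff: 3.07 (Bonferroni 3.09).
- Power per protein: P(Z > 3.07 − 3.68) = 0.73.
- P(at least 15 of 25) = 0.86, against about 0.90 stated. A correlation of 0.05 gives 0.89, and independent proteins 0.94. The correlation structure is not given, so I draw no conclusion from the gap.

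The 60% is the metformin-arm figure in 16.1.1; pooling the arms gives a higher share. That is a separate matter, and the point here does not rest on it.

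**2. Breasts available.** 25% of 88 women give one breast and 75% give two: 22 + 66 × 2 = 154. A woman's single breast must be atypical for her to qualify, so clear breasts come only from the 66.

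**3. Share of clear breasts (assumption).** The documents give no figure. As a rough check, section 16.1.1 expects 96 of 177 women to qualify (54%). Treating that as the cytology pass rate, with 75% of randomized women giving two breasts, implies about 28% clear breasts at a between-breast correlation of 0.3, and 21-33% for correlations from 0.6 down to 0. I take 20-35% as plausible, and work below with 48 of 154 (31%), leaving 106 atypical at entry.

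**4. How entry status leaks into the outcome.** Further assumptions: month-12 atypia in breasts atypical at entry is 90% on placebo and 60% on metformin (the woman-level rates of 16.2.1.1), averaging 75%. In breasts clear at entry it is 10% (the conversion rate).
- Atypical at month 12: 106 × 0.75 + 48 × 0.10 = 79.5 + 4.8 = 84.3. Share atypical at entry: 79.5 / 84.3 = 0.943.
- Clear at month 12: 154 − 84.3 = 69.7. Share atypical at entry: 26.5 / 69.7 = 0.380.
- Difference: 0.563.

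A protein shifted by d SD with entry atypia, and unrelated to persistence, thus differs by 0.563 × d between the month-12 groups. The standard error is √(1/84.3 + 1/69.7) = 0.162. The variance within a month-12 group becomes 1 + d² × (84.3 × 0.943 × 0.057 + 69.7 × 0.380 × 0.620)/154 = 1 + 0.136 d².
- d = 0.5: z = 0.281 / 0.162 = 1.74, or 1.71 after dividing by √1.034. P(Z > 3.07 − 1.71) = 0.087, so about 2.2 of 25 such proteins flagged.
- d = 0.8: z = 0.450 / 0.162 = 2.78, or 2.67 after dividing by √1.087. P(Z > 0.40) = 0.34, so about 8.6 of 25.

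Full simulation gave means of 2.2 and 8.3.

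**5. Chance of at least one flag.** This needs simulation because proteins and breasts are correlated: max-T permutation at 10%, between-breast correlation 0.3, between-protein correlation 0.1, 25 proteins tied to entry atypia, none to persistence. Two separately coded runs, with 31% and about 29% clear breasts, gave (one figure where only the first was run):

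| Shift with entry atypia | 10% conversion | 30% conversion |
|---|---|---|
| 0.3 SD | 35% | 26% |
| 0.5 SD | 78%, 80% | 51%, 45% |
| 0.8 SD | 98%, 98% | 83%, 79% |

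A wider grid (25-75% of two-breast women with one atypical breast, conversion 10-25%, shift 0.5-0.8 SD) ran from 24% to 99%. Its middle case (33 clear breasts, 21%; 10% conversion; 0.8 SD) gave 90%, with about 4 of 25 proteins flagged.

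**6. Controls.** With no link between protein and entry atypia: 8-11%. With one atypical breast per woman: 12%. Restricted to breasts atypical at entry: 8-13%. The excess therefore comes from including breasts that were clear at entry.

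**The case against.** The strongest reply is that the test does what it says. Objective 2.2.4 and the heading of 16.2.2.4 speak of presence of atypia, and a protein that marks atypia at entry really is associated with presence at month 12. Rejecting that null is correct, and the no-link runs hold the nominal 10%. This stands. A reader might infer that the plan fails to control family-wise error; for the null as written, it does control it. What remains is that the controlled list does not answer the question about persistent atypia on which the same section bases its power.

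Second, a reader might infer that baseline is ignored. It is not: the per-protein multivariate model contains baseline Masood scores, and a change-from-baseline analysis of the score is also planned. The gap is narrower: family-wise control is stated beside the unadjusted test and is not extended to the adjusted one.

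Third, section 16.2.1.2 speaks of eligible breasts without defining them. If that meant only breasts atypical at entry, and applied here, the problem would largely vanish. Section 16.2.2.4 does not say so.

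Fourth, phosphoprotein expression is labelled exploratory in sections 2.3.1 and 14.1, and neither the primary endpoint nor treatment depends on it. That limits the weight of the point but does not remove it.

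**Conclusion.** The point holds as a limit on interpretation, with a cheap remedy. The test that carries the 10% family-wise claim mixes two questions, and a flagged protein may reflect only atypia at entry. The chance of at least one such flag is roughly 25-40% at 0.3 SD, 45-80% at 0.5 SD and 80-98% at 0.8 SD, against about 10% when only breasts atypical at entry are used. These figures assume about 30% clear breasts, 10-30% conversion, and 25 proteins linked to entry atypia and none to persistence. None of these values is in the documents; only the 0.8 SD and the count of 25 echo the plan's power text, where they describe a different association. Fewer clear breasts or weaker links lower the figures.

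A reader might go further and conclude that the protein list would mostly re-identify baseline atypia. The documents do not support that: they say nothing about how strongly these proteins relate to entry atypia, and the simulations set every persistence effect to zero, so they cannot show what share of a real list would be spurious.

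**What to change.** State in 16.2.2.4 that the permutation family-wise control applies to one of the following:
- the protein coefficient in the adjusted model already planned, permuting outcomes within baseline-atypia strata and keeping a woman's two breasts together; or
- the same test restricted to breasts with a baseline Masood score of at least 14, again permuting whole women.

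Keep the unadjusted all-breast correlation as descriptive, and do not report its hits as predictors of persistence. Use the same rule for the month-24 analysis.

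The cost is SAP wording and code; no new data are needed. The restricted set has about 106-110 of 154 breasts. A reader might fear that this undercuts the stated 90% power, but that figure assumes one breast per woman, or 88, and every woman has at least one atypical breast. With 106 breasts (70 women giving one, 18 giving two) and a correlation of 0.3, the design effect is 1 + 0.3 × ((70 + 18 × 4)/106 − 1) = 1.10, so about 106 / 1.10 = 96 effective breasts. Only the remark that two-breast women will raise the power further is weakened.

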#### **16.0 STATISTICAL CONSIDERATIONS AND METHODOLOGY**

#### 16.1 Study Design

#### **16.1.1 Study Populations**

A total of 177 premenopausal women will be pre-registered, among which 96 patients with atypia (Masood Score 14-17) on RPFNA at baseline are expected to be randomized between

Metformin arm and placebo control arm. It is expected that the accrual rate will be 1 patient per month and that accrual will be completed about 8 years after study activation. The randomization will be stratified for known BRCA mutation (BRCA1 or BRCA2 mutation vs. no mutation), prior excisional biopsy (atypical epithelial hyperplasia, atypical lobular hyperplasia, flat epithelial hyperplasia vs. DCIS vs. LCIS), and baseline fasting insulin > 2x ULN vs.  $\leq 2x$  ULN.

At 12 months the women in the placebo arm will be allowed to take metformin. Based on experience from 300 women undergoing serial RPFNA at Duke, it is anticipated that approximately 40% of women who are randomized to the metformin arm will have disappearance of atypia at 12 months and 60% will have persistent atypia. The estimated drop-out rate is 5% at 6 months and 10% at 12 months. Over 98% of women with atypia will have atypia on repeat RPFNA on the non-metformin arm.

We propose to test RPFNA on both right and left breasts at, 12 and 24 months after registration/randomization for the presence or absence (Masood score  $\leq$ 13) of atypia by Masood Cytology Index Score. The RPFNA at 24 months is optional for women who continue on the placebo control arm and will not receive metformin. The outcomes collected at 24 months will be exploratory. In analysis, we will consider taking a transformation, such as logarithm, of positive variables in order to improve the normality and variance stabilization. Among the 96 randomized patients, we expect that about 10% of patients will drop out at month 12. So, the power analyses are based on N= 88 patients (44 per arm).

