#### **16.2.1.1 Primary Analysis**

Multiple Masood scores from each breast will be averaged for each time point. The primary endpoint of the study is the binary outcome of atypia (Masood score  $\geq$  14). In this analysis, the sampling units will be women, so that, if a woman has atypia in one breast and no atypia in the other breast, this woman will be called atypia. Presence of atypia at month 12 will be compared between two arms using the chi-square test in univariate analysis, and regressed on group indicator, age, race, stratification factors, and baseline Masood score using logistic regression in multivariate analysis. As an exploratory analysis, we will also conduct a regression analysis including the timing of baseline RPFNA (intraoperative vs. in clinic) and the number of breasts with atypia at baseline in addition to these covariates. With 44 women per arm, the primary analysis has 90% of power to detect a difference of 90% vs. 60% of atypia between placebo and metformin arms at month 12 by a chi-square test with alpha=5%.

In order to address the worst score rule, we will repeat above analyses using the maximum, instead of average, Masood score from each breast.

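### The RPPM power statement in Section 16.2.2.4 applies the metformin-arm persistence rate (60%) to both arms pooled; the plan's own rates give 75% or 79% of women, so its 90% is not an established floor

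*Combined protocol and SAP*

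**What the plan says.** Section 16.2.2.4 serves secondary objective 2.2.4. It pools the arms: "We will combine data set of metformin and no-metformin groups (N = 88". The unit is the breast: "use the breasts as the sampling units in this analysis". For the analysis of atypia at month 12 it states "We expect that about 60% of the women will have persistent atypia at 12 months". It then claims about a 90% probability of detecting 15 or more proteins when 25 of 50 have an effect of 0.8 SD, with two-sided tests and the family-wise error rate held at 10% by permutation. The condition is "Assuming that each woman contributes samples from only one breast and the proteins have correlation coefficient of 0.1". No figure is given for the breast-level analysis itself, only the remark that since "about 75% of women are expected to contribute samples from both breasts to the study, the real power for this analysis will be higher".

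Elsewhere the plan gives persistence by arm. Section 16.1.1 expects that about 40% of "women who are randomized to the metformin arm will have disappearance of atypia at 12 months and 60% will have persistent atypia". For the other arm it says "Over 98% of women with atypia will have atypia on repeat RPFNA on the non-metformin arm". The primary power statement in Section 16.2.1.1 uses "a difference of 90% vs. 60% of atypia between placebo and metformin arms at month 12". Section 16.2.1.1 also counts a woman as having atypia if either breast shows it.

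**The concern.** The 60% in the pooled statement is the rate that Section 16.1.1 gives for metformin alone. For 60% to hold across both arms with metformin at 60%, placebo would also have to be at 60%, which means no treatment effect. Neither placebo rate in the plan allows that.

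The split matters because power to compare protein values between women with and without atypia depends on the smaller group. At 60% about 35 of 88 women are without atypia; at 75% or 79% about 22 or 18 are. The one-breast 90% also serves as the base from which the plan argues that real power is higher. If the base is not 90%, that argument does not guarantee 90%, and a reader who sees few significant proteins could take this for stronger evidence of no association than it is.

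**Working it through.** **Inputs.** N = 88, 44 per arm (Section 16.1.1). Metformin persistence 60%; placebo 90% (Section 16.2.1.1) or over 98%, taken as 98% (Section 16.1.1). From Section 16.2.2.4: 50 proteins, 25 true at 0.8 SD, correlation 0.1, two-sided family-wise error 10%, success defined as 15 or more detected. About 75% of women contribute two breasts, so 22 women have one breast and 66 have two: 22 + 2 × 66 = 154 breasts.

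**Pooled woman-level rate.** (0.60 + 0.90)/2 = 0.75, or 66 women with and 22 without atypia. (0.60 + 0.98)/2 = 0.79, or about 70 and 18.

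**One-breast power.** For a true protein the test statistic has mean 0.8 × √(n1 × n0/88):
- 53/35: 0.8 × √21.08 = 3.67
- 66/22: 0.8 × √16.5 = 3.25
- 70/18: 0.8 × √14.32 = 3.03

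The joint probability was simulated with exchangeable correlation 0.1. The cut-off is the 90% quantile of the largest absolute null statistic: 3.07 for the normal approximation, 3.15-3.18 for the two-sample t. The plan's own figure comes first.

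| Split | Normal, single-step / step-down | t, single-step / step-down |
|---|---|---|
| 53/35 (60%) | 0.85 / 0.90 | 0.78 / 0.86 |
| 66/22 (75%) | 0.49 / 0.59 | 0.40 / 0.50 |
| 70/18 (79%) | 0.28 / 0.37 | 0.22 / 0.30 |

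The stated figure of about 90% is thus reproduced at 60% (normal, step-down). A t test with correlation in blocks of 10 gave somewhat lower single-step values at 75% and 79% (0.34 and 0.15), but only 0.835 at 60%.

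**What the lower rows assume.** The 75% and 79% are rates for women, with atypia in either breast counting. Using them for one sampled breast assumes that this breast always shares the woman's status. Let d be the share of two-breast women with atypia who have it in one breast only, with one breast sampled at random. The rate in the sampled breast is p × [0.25 + 0.75 × (1 − d/2)] = p × (1 − 0.375d).

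| d (assumed) | Rate, p = 0.75 | Power, single-step / step-down | Rate, p = 0.79 | Power, single-step / step-down |
|---|---|---|---|---|
| 0 | 0.750 | 0.49 / 0.59 | 0.790 | 0.30 / 0.40 |
| 0.3 | 0.666 | 0.77 / 0.83 | 0.701 | 0.68 / 0.76 |
| 0.5 | 0.609 | 0.85 / 0.90 | 0.642 | 0.81 / 0.87 |

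These are normal approximations, good to about 0.02. The d = 0 entry for 79% uses the exact rate, not the rounded 70/18. With the t test at d = 0.5 the values are 0.79/0.85 and 0.73/0.81.

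**Planned breast-level analysis.** Let r be the between-breast protein correlation. The number of breasts with atypia is n1 = 22p + 66p(2 − d), and n0 = 154 − n1. In SD units, the variance of the mean difference under working independence is

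[22p + 66p(1 − d)(2 + 2r) + 66pd]/n1² + [22(1 − p) + 66(1 − p)(2 + 2r) + 66pd]/n0² − 2r × 66pd/(n1 × n0).

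Example with p = 0.75, d = 0, r = 0.3: n1 = 115.5, n0 = 38.5; 145.2/115.5² + 48.4/38.5² = 0.0435; 0.8/√0.0435 = 3.83; probability 0.93.

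| r, d (both assumed) | Normal approximation, 75% / 79% | Sandwich errors with simulated cut-off, 75% / 79% |
|---|---|---|
| 0.3, 0 | 0.93 / 0.81 | 0.81 / 0.52 |
| 0.3, 0.2 | 0.99 / 0.99 | 0.98 / 0.94 |
| 0.7, 0 | 0.64 / 0.44 | 0.39 / 0.15 |
| 0.7, 0.2 | 0.95 / 0.91 | 0.89 / 0.85 |
| 0.7, 0.3 | 0.99 / 0.98 | 0.97 / 0.95 |

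All are single-step. The plan gives neither r for protein values nor d. Section 16.2.1.2 uses 0.3 between breasts, but for Masood scores.

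**The case against.** The strongest reply is that 60% may be about right for the unit that is analysed. A woman counts as having atypia if either breast does, so the rate per breast is lower than the rate per woman. Sections 1.3.2 and 16.2.2.2 report or expect little agreement between breasts in Masood score. With d = 0.5 the rate over all 154 breasts is 0.589 or 0.621, the rate in one sampled breast is 0.609 or 0.642, and one-breast power comes back close to the plan's figure. This part stands: 0.4-0.6 and 0.2-0.4 cannot be quoted without the assumption of full concordance. It does not rescue the text, which speaks of women, states no breast-level rate and gives no concordance of atypia.

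A reader might go further and infer that the 90% was computed from the wrong 60%. The documents do not establish that. A 44/44 split also gives about 0.89-0.90 (normal single-step, or t step-down), so the origin of the figure is unproven.

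A reader might also infer that the planned analysis is underpowered. The documents do not support that either. With 154 breasts, every run at d of 0.3 or more is 0.95 or higher. The low values need d near zero, and the lowest also need r = 0.7; near-complete concordance sits poorly with the low between-breast agreement the plan expects.

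**Conclusion.** Wrong as written, with low impact. The pooled 60% contradicts the plan's own arm rates, which give 75% or 79% of women. On the stated one-breast basis, the probability of 15 or more detections is then about 0.4-0.6 or 0.2-0.4 if the sampled breast always shares the woman's status. It approaches 0.9 only under substantial discordance between breasts, which the plan does not state. The claim of higher real power therefore starts from a floor that has not been established.

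The textual mismatch is certain. The size of the shortfall is not, because it depends on a concordance the plan does not give. Breast-level power is simply unstated: it may be below 90%, or 90% or more. The point touches one power statement for one secondary objective. Sample size, primary power and primary analysis are unaffected.

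**What to change.** 1. Replace the 60% with the pooled woman-level rate: 75% on the 90%/60% rates, or 79% on the 98%/60% rates. Alternatively, define 60% as a breast-level rate and justify it.
2. Restate the one-breast probability with the assumed between-breast concordance of atypia written next to it. Or state the effect size that keeps about 90%: with full concordance, about 0.95 SD at 75% and 1.0-1.05 SD at 79%.
3. Replace the unquantified claim of higher power with a breast-level figure that states its assumed between-breast RPPM correlation and atypia concordance.

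The cost is one recalculation and a few sentences in Section 16.2.2.4. The one-breast figure may become less favourable; the breast-level figure may still be 90% or more. Patients, assays, sample size and the primary analysis do not change.
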